12C) I. What are the arrangements for day-to-day management of the trial? Each clinical centre will have a centre dietitian who will be responsible for preparing hospital ethics committee protocols, protocol modification and adverse event reporting. The dietitians will also alert the centre physicians to any concerns, which may need medical action. They will arrange advertising, answer resulting phone calls and screen potential participants, set up information sessions, and participant screening visits and later study visits, coordinate physician and blood technician schedules, and make appointments for diagnostic tests (e.g. MRI). At clinic visits they will encourage consumption of the appropriate amounts of the key ingredients on the dietary portfolio and adherence to whole grain cereals on the control diet, check 7-day diet records and, if necessary, alter the diet plan accordingly. Tests in each clinical center will be under the supervision of a physician with an expertise in exercise testing. Previous cardiac history as well general health information will be made available for the safe conduct of exercise testing and to those conducting exercise testing. The patients' personal health information will be transferred through File Transfer to the alternate stress test location (Toronto Cardiac Clinic) and the results of the exercise testing will be sent back to us via study ID and ONE Mail. The physician does not

Name of Nominated Principal Applicant	(V21) September 2, 2022
[name]	
Full project title MRI – Enhanced Dietary Portfolio plus Exercise on Cardiovascular Risk	

Combined Study Protocol

have to be a cardiologist and does not necessarily have to be present in the exercise lab while the testing is being done; as long as he/she is present on the floor and easily reachable. Each center will also have a certified kinesiologist (0.15 FTE) who will provide assistance to the centre dietitian for the conduct/coordination of the study. In addition, the kinesiologist will be responsible for the assessment of baseline physical activity levels, cardiorespiratory fitness and readiness to change for all local participants and prepare an individualized intervention aiming at reducing sedentary behaviors, increasing the number of daily steps to 10,000 and increase cardiorespiratory fitness through the prescription of 150 weekly minutes of moderate to vigorous intensity endurance exercise depending on baseline fitness. Together with the part-time clerk, they will enter dietary, laboratory, anthropometric and blood pressure data on the data templates provided by the Applied Health Research Centre (AHRC) of the Li Ka Shing Institute which is responsible for electronic data storage and quality control of the data. Together with the part-time clerk, they will enter dietary, laboratory, anthropometric and blood pressure data on the data templates provided by the Applied Health Research Centre (AHRC) of the Li Ka Shing Institute which is responsible for electronic data storage and quality control of the data. The dietitian at the Toronto site will also act as the study coordinator responsible for coordination between the 4 sites.

Study charts will be organized by the part-time study clerk together with physician notes and consent forms. They will assist the dietitians with all aspects of recruitment, with diet history coding, data entry, and quality control. Centre PIs will be available throughout the study to discuss study issues with the site dietitian as they arise and will meet on at least a daily basis.

Blinded to treatment, MRI scan data will be read and the data processed by the research assistant, Postdoctoral Fellow and MSc students under [name] at the Sunnybrook Vascular Imaging core facility.

Food Supply:

Study participants will be able to pick up study bread and other food supplies from our clinic centre in-person or by curbside pick-up during pandemics as availability permits from study sponsors. We anticipate centre pick-ups will be no more than once per month and will likely replace a normal shopping outing. The study bread will also be available for purchase directly from a local baker in store or by curbside pick-up; and we will cover the bread cost so no contact is necessary for payment during pandemics. Study participants may be also be able to order food products directly from study sponsors using a study code for a subsidized cost in order to have products delivered to their home.

Data Management: Data will also be organized by the recently initiated (2009) AHRC (www.ahrconline.com) for clinical trial support, of the Li Ka Shing Knowledge Institute of St. Michael's Hospital, which has a clinical trials unit designed precisely to support such studies. The MRI studies will generate a very large volume of imaging data. Storage of anonymised, catalogued, image data will be located at the Sunnybrook Health Sciences Centre MRI Research Unit with links to the AHRC, using blade-server technology to permit ease of upsizing when future projects are added to the MRI program. Post-processing will take place at the Sunnybrook Vascular Imaging core facility. Image data will be reduced to quantitative data that will be entered into the Case Report Forms that will be developed prior to study commencement. The clinical database will be held centrally at St. Michael's Hospital's AHRC in collaboration with the Li Ka Shing Institute. The data management system also allows for MRI images to be

Name of Nominated Principal Applicant	(V21) September 2, 2022
[name]	
Full project title MRI – Enhanced Dietary Portfolio plus Exercise on Cardiovascular Risk	

Combined Study Protocol

uploaded onto a web-based system with centralized servers in a secure data centre. Both the data management system and the physical infrastructure where the hardware will reside exceed international privacy and security standards. This system ensures direct, secure access to data via a dedicated portal to the Institute server, which can be accessed by the internet, and enables information storage, retrieval and sharing. The system will be organized by the Li Ka Shing Knowledge Institute IT group, whose statistical group will also provide support. AHRC, will provide overall clinical data management support through the MediData RAVE™ data management software (www.mdsol.com) which is being used for over 10 studies run through AHRC, including 3 currently funded CIHR multi-centre trials.

12C) II. What will be the role of each principal applicant and co-applicant proposed?

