The kinesiologist will work with participants in the structured exercise arms using behavioral strategies to develop and support a plan that aims to achieve the target of 150 min/week of physical activity or exercise in 3 or 5 sessions weekly (vigorous, moderate or mild depending of goals and tolerance) in keeping with maximum achievable goals of participants (19). When necessary, appropriate walking speed/intensity will be demonstrated on a treadmill by the kinesiologist. The program will also target a goal of achieving at least 10,000 steps daily recorded on their pedometers. We expect from previous experience that the vast majority of participants will have a much lower step count than the 10,000 step target at baseline but that most of them will be able to reach this target within 3 months (20). The routine exercise groups will receive standard of care for individuals being seen by a general practitioner. Specifically they will be advised to achieve the current recommended targets for daily physical activity and educational material published by Health Canada (Canada's Physical Activity Guide, Health Canada, Please see Appendix 4). Participants in the routine exercise arms will receive an exercise diary and the 7-D diet histories including the treadmill tests at the start and end of each 1 year period. They will not receive the more frequent, targeted visits with a certified kinesiologist.

12B) III. What are the proposed practical arrangements for allocating participants to trial groups? Participants who meet inclusion criteria will be randomized after stratification by centre and sex, due to the later onset of CHD in women. Random permuted blocks of varying

Name of Nominated Principal Applicant	(V21) September 2, 2022
[name]	
Full project title MRI – Enhanced Dietary Portfolio plus Exercise on Cardiovascular Risk	

Combined Study Protocol

sizes (≤ 10) will be used to eliminate the possibility of predicting a future allocation leading to selection bias. The treatment allocation will be revealed to the dietitian using the web-based system after stratum entry, in the presence of the participant during the zero time visit.

12B) IV. What are the proposed methods for protecting against other sources of bias?

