Dietary Assessment: Diets will be analyzed using a program based on USDA data (ESHA) (32) (Please see Appendix 8A for details) and through metabolomics assessment, to help identify objective biomarkers of specific foods consumed by the participants which is not prone to the

Name of Nominated Principal Applicant	(V21) September 2, 2022
[name]	
Full project title MRI – Enhanced Dietary Portfolio plus Exercise on Cardiovascular Risk	

Combined Study Protocol

same measurement and reporting errors of traditional self-report diet tools at baseline and year one.

Analytical Techniques: Serum lipids and C-reactive protein (CRP) will be measured at each centre on fasting serum. LDL-C will be calculated using the Friedewald equation (33). Serum lipid standards (Solomon Park Research Laboratories, Kirkland, Washington) will be used to quality control the lipid analyses at the 3 collaborating sites. (Please see Appendix 8A for details). IMT will be measured by B-mode Carotid Ultrasound at 12 carotid artery segments (1-cm long) of the near and far walls of the internal, bifurcation and common left and right carotid arteries. Screening will follow the protocol of the SECURE Trial (34, 35). Magnetic Resonance Imaging (MRI) will follow standardized protocol in terms of Scanner, Coils, Sequences, and Software: MRI carotid scans will be performed at the 3 centres using 3.0 T whole-body scanners and using a standard protocol with a phased array neurovascular coil and read at a central location (Sunnybrook). (Cardiovascular imaging software: MRI-PlaqueView 2.0, VP Diagnostics, Inc., Seattle, WA). The carotid flow divider will be used as the iso centre of the data volume and carotid wall parameters 25mm above and below this point will be included in the analysis. Semi-automated vessel wall boundaries will be defined using Q-plaque software (Medis, the Netherlands) (Please see Appendix 5).

Metabolomics analysis for dietary assessment: Metabolites will be analyzed in de-identified plasma samples at the Broad Institute at MIT and Harvard. The metabolites will be measured in plasma by LC-MS, using HILIC-pos method to measure polar metabolites and the C8-pos method to measure lipids.

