We have selected -106.5mm^3 as the effect size treatment difference at year 3 in MRI assessed plaque volume based on a study by Migrino et al. that demonstrated a reduction in plaque volume following increased statin dosage (36). This study demonstrated a 60mm^3 reduction in plaque volume for a 0.31mmol reduction in LDL-C (36) over a 6-month period. Our own recent portfolio study (**JAMA 2011**) demonstrated a 0.49mmol/L LDL-C reduction at 6 months on the portfolio arm after allowance was made for 0.16mmol/L LDL-C reduction on the control. Our planned study will last for 3 years and our unpublished open label single phase dietary portfolio study of 61 participants indicated a further reduction of 0.06mmol/L in LDL-C over the 6 month to 3 year period. We have added this further reduction to our JAMA 2011 value (4), giving an overall 0.55mmol/L LDL-C reduction. This 0.55mmol/L LDL-C reduction would correspond to a between treatment difference of 106.5mm^3 in plaque volume, according to the findings of Migrino and colleagues and therefore will be our effect size (36).

ii) SD was determined to be 276mm^3 by using a pooled SD from the Migrino paper (baseline: 300mm^3 , end of treatment: 331m m^3 , $n=26$) (36), a [name] cross-sectional assessment (210mm^3 , $n=10$) (37), and our own preliminary data from our CIHR diabetes study at baseline and 1 year (baseline: 227mm^3 , 1-year: 225mm^3 , $n=16$) (pooled data, blinded to treatment). We used the two papers since they assessed individuals with more modest plaque, similar to the population to be recruited. These SDs spanned the range of SDs emerging from our current CIHR funded glycemic index MRI study.

iii) Dropout: Our recent portfolio diet study had a dropout rate of 23% (**JAMA 2011**) (4). However, our current CIHR funded low GI diet study with similar ultrasound and MRI protocol has only had a 10% (7/69) dropout in the 1-year period (6/7 dropped out in the first 3 months). We therefore consider our dropout rate will be between 10% and 25% and most likely below 20% (i.e. >80% retention), which has traditionally been considered as providing a high level of evidence, e.g. National Institute for Health and Clinical Excellence (NICE), Grading of Recommendations Assessment, Development and Evaluation (GRADE), etc (38-41). However, we have allowed for 30% dropout in the sample size calculation to ensure that we have adequate power.

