iv) Screening: Only when there is measurable thickening in intima-media thickness ($>1.0\text{mm}$) can significant change be reliably detected as shown with 2 recent statin trials (42, 43) and a diet trial (22). Since it is estimated that between 30 to 50% of the non-diabetic population in our participants' age range have measurable arterial thickening (22, 44-46), we should be prepared to recruit and screen up to 3 times as many participants as we finally randomize to ensure measurable arterial thickening in our participants.

v) Sample size Calculation: We are using our previous power calculation (see below) for the present factorial design since we are advised that the final numbers required remain the same if there is no intended interaction between the two treatments. Using two-sample t-test, we would require 105 participants per treatment arm to detect a significant effect size of 106.5mm^3 (i.e. an end of treatment difference based on the expected relative cholesterol reduction in test vs. control, considering study length and dropout) with an end of treatment SD of 276mm^3 ($\alpha=0.05$, $1-\beta=0.80$)(47). However, since our final data will be analyzed by ANCOVA, we have used the ANCOVA sample size calculation to determine our final sample size. Due to the lack of r-values in the literature, and our expected recruitment of participants with preclinical vascular disease in a narrow range of screening arterial thickening, we anticipate only a modest degree of correlation

Name of Nominated Principal Applicant	(V21) September 2, 2022
[name]	
Full project title MRI – Enhanced Dietary Portfolio plus Exercise on Cardiovascular Risk	

Combined Study Protocol

between end and baseline values. We have therefore used a correlation of 0.6 in our ANCOVA sample size calculation which yields 67 participants required per arm (48). Therefore, assuming 30% dropout rate over 3 years (Please see Section 12B) XIV), we will need to randomize a minimum of 194 participants (81 per arm) for the proposed study. We will therefore screen and scan three times this number to ensure measurable arterial thickening, i.e. 576 theoretically eligible participants of whom one third will be randomized.

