Secondary Measures: A published power calculation from a major meta-analysis of the literature indicated that with 130 completers we will be able to detect a $\approx 10\%$ between treatment difference in maximum percentage lipid rich necrotic core (49). Reliable estimates for intraplaque hemorrhage are not currently available due to the newness of this now clinically relevant MRI measurement. However from biological considerations, power requirements are likely to be similar to those for the lipid rich necrotic core. In previous studies 120 participants have been sufficient to detect 4% changes in BP and pulse (**Arch Intern Med. 2012**) (50). No participant with previously acceptable LDL-C levels rose above the predetermined cut-point requiring statin treatment. Data were therefore not available on which to base a power calculation.

Tertiary Measures With 194 participants we will be sufficiently powered to detect between treatment differences of of 8.5% in LDL-C, 6.9% in total cholesterol:HDL-C ratio, and 4.5% in CRP (**JAMA 2011, JAMA 2003**) (4, 14).

12B) XII. (a) What is the planned recruitment rate? We plan to screen 582 subjects/1.5y, 292 in Toronto and 145 in each of the other centres (to randomize 194).

Although our study was closed at the time we reached our recruitment number of 194, a further 60-70 potential participants were still in the pipeline due to the length of time the recruitment process takes. Since they had signed the consent form, we felt it inappropriate to tell them they were no longer needed. Therefore our new total for the Toronto site is 160 for a total of 260.

12B) XII. (b) How will the recruitment be organized? -4 methods of recruitment will be used:

- 1) Advertising in newspapers and on the Toronto subway system.
- 2) From previous studies—contacting past study participants who had consented to being contacted for future studies. They will be contacted by mail followed by a telephone call in 2 weeks if no response.
- 3) Advertising (using REB approved study poster) in family doctors clinics and specialized clinics at St. Michael's Hospital and hospitals in the Greater Toronto Area having first obtained permission from the relevant clinics. The specialized clinics will include Lipid and Diabetes clinics, family doctors' clinics, cardiology, vascular (CATH) labs, and cardiac rehabilitation clinics.

Initial screening will take place by telephone.

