a. 12B) XV. How many centres will be involved? Three recruitment sites will be involved: Institute of Nutraceuticals and Functional Foods, Laval University, Quebec; Healthy Heart Lipid Clinic, St. Paul's Hospital, Vancouver; and the Clinical Nutrition and Risk Factor Modification Centre, St Michael's Hospital or the David Naylor Building at the University of Toronto, and North York Family Health Team, North York General Hospital will be the recruitment clinics in Toronto. The MRI unit, Sunnybrook Health Science Centre, Toronto, Ontario, will be responsible for the interpretation of MRI scans. Robarts Institute, Western University, will be interpret and analyze screening US data. The Department of Biostatistics, McMaster University will oversee statistical aspects of the trial. The Nutritional Sciences Department, Faculty of Medicine, University of Toronto will also be involved in the assessment and quality control of recorded dietary data for all centres. We are adding an additional stress test clinic site, Toronto Cardiac Clinic because the stress test clinic at St. Michael's Hospital is not able to accommodate all of our research study patients because of the Covid-19 pandemic. Participants randomized (as opposed to screened) will be 98 at the Toronto site and 48 each at the other sites.

12B) XVI. What is the proposed type of analysis? An ANCOVA linear regression model will be used with the 3 year value as the outcome, treatment and sex as main effects and baseline as a covariate. In the intention-to-treat analysis, we will assume that data are multivariate, normally distributed and missing data are missing at random (MAR). For multiple imputations, the mean of 5 sets of generated data will be taken; this process will generate data for missing values, standard errors, and 95% confidence intervals [CI]. For example, using LDL-C

Name of Nominated Principal Applicant	(V21) September 2, 2022
[name]	
Full project title MRI – Enhanced Dietary Portfolio plus Exercise on Cardiovascular Risk	

Combined Study Protocol

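### Randomisation is stratified by centre and sex, but the primary ANCOVA omits centre; if centres differ after baseline adjustment, the test is mildly conservative (minor)

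*Protocol*

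**What the plan says.** Protocol section 12B) III sets the allocation: "Participants who meet inclusion criteria will be randomized after stratification by centre and sex", using permuted blocks of varying size up to 10 within strata. With three centres and two sexes there are six strata.

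Section 12B) XVI gives the only outcome model in the document. It is an ANCOVA on the 3-year value, with "treatment and sex as main effects and baseline as a covariate". Centre is not a term, and no other section adds it. Site appears twice more in the analysis text: as something that did not predict missing data in an earlier study (12B) XVI), and as a possible exploratory analysis (12B) XVIII). Neither is an adjustment of the primary comparison.

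On centre sizes, section 12B) XV says: "Participants randomized (as opposed to screened) will be 98 at the Toronto site and 48 each at the other sites". Section 12B) XII (a) later revises this: "Therefore our new total for the Toronto site is 160 for a total of 260". On measurement, section 12B) IX has MRI done at all three centres, "using a standard protocol with a phased array neurovascular coil and read at a central location".

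**The concern.** The usual rule is that a factor used to restrict randomisation also goes into the analysis model. Here one stratification factor (sex) is included and the other (centre) is not. The section lists its terms, so this is a stated mismatch and not a detail left open for a later analysis plan.

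Blocking within centre keeps the groups nearly equal at each centre, so differences between centres almost cancel from the treatment contrast. Without a centre term, those differences are still counted as residual noise. The model-based standard error then exceeds the true sampling variation of the estimate, the confidence interval is wider than it need be, and the test rejects less than 5% of the time under the null. What is at stake is a little precision that the stratified design has already secured. It is not the validity of the result.

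**Working it through.** **Inputs.** Effect 106.5 mm³, SD 276 mm³, two-sided α = 0.05, power 0.80, baseline-to-end correlation 0.6 and 30% dropout (section 12B) XI). Total 194 (12B) XI) or 260 (12B) XII (a)). The comparison is the diet main effect, half the completers against the other half. The protocol gives no figure for f, the share of the variance left after baseline adjustment that is due to centre, so f = 0, 2 and 5% are assumptions.

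**The plan's own figures.** 2 × (1.96 + 0.842)² × 276² / 106.5² = 105.4 per group (stated: 105). Multiplying by 1 − 0.6² = 0.64 gives 67.5 (stated: 67). Taking 68, 2 × 68 / 0.7 = 194.3 (stated: 194). The plan's calculation reproduces.

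**Standard error.** Residual SD = 276 × √(1 − 0.36) = 220.8 mm³.
- At 260: 0.7 × 260 = 182 completers, 91 per side. SE = 220.8 × √(2/91) = 32.73. R = 106.5 / 32.73 = 3.254.
- At 194: 135.8 completers, 67.9 per side. SE = 37.89, R = 2.810.

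**Effect of omitting centre.** Let k = √(1 − f). The formulas treat centre as exactly balanced among completers.
- If the SD of 276 already contains centre variance: power without centre = Φ((R − 1.96)/k); with centre = Φ(R/k − 1.96); half-width = 1.96 × SE without and 1.96 × SE × k with.
- If it does not: power without centre = Φ(R − 1.96/k); with centre = Φ(R − 1.96).
- In both cases, type I error without centre = 2 × (1 − Φ(1.96/k)).

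Section 12B) XI ii) pools the SD from two published studies and "our own preliminary data from our CIHR diabetes study at baseline and 1 year". It does not say whether centre variance is inside it, so both cases are shown.

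| | f = 0 | f = 2% | f = 5% |
|---|---|---|---|
| 260, SD includes centre: power without / with (%) | 90.2 / 90.2 | 90.4 / 90.8 | 90.8 / 91.6 |
| 260, SD excludes centre: power without / with (%) | 90.2 / 90.2 | 89.9 / 90.2 | 89.3 / 90.2 |
| 260, SD includes centre: half-width without / with (mm³) | 64.2 / 64.2 | 64.2 / 63.5 | 64.2 / 62.5 |
| 194, SD includes centre: power forgone (points) | 0 | 0.5 | 1.4 |
| 194, SD excludes centre: power without / with (%) | 80.2 / 80.2 | 79.7 / 80.2 | 78.8 / 80.2 |
| Type I error without centre (%) | 5.0 | 4.8 | 4.4 |

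**Simulation.** Dropout partly undoes the balance, so the formulas were checked by simulation. The design had blocks within centre × sex, 160/50/50 participants (the 50/50 split is assumed), half of each sex and blocks of 4 or 8 (also assumed), 30% random loss, and 10,000 runs per cell. With 260 and the SD including centre variance, power without / with centre was 90.3/90.2, 90.0/90.2 and 90.1/90.9% at f = 0, 2 and 5%. Two further simulations put the gain from adding centre between −0.4 and 0 points at f = 0, between 0 and 0.4 at 2%, and at 1.0 at 5%. Type I error without centre at f = 5% was 4.7%, closer to nominal than the formula's 4.4%. A separate simulation at 194 showed no bias in the effect estimate with or without centre.

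**How large is f likely to be?** The smallest gap between Toronto and the other centres that produces a given f is √(f × 220.8² / (p(1 − p))), with p = 160/260. This gives about 64 mm³ for f = 2% and about 101 mm³ for f = 5%, both after baseline adjustment.

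**The case against.** The strongest reply is that nothing the trial concludes is shown to change. The test remains valid and unbiased, power at 260 is about 90% either way, and at f = 0 the extra term costs a trace of power. The quantity that drives the effect is assumed, and the protocol points to a small value: 3.0 T scanners at every centre, a standard protocol, blinded central reading, and a baseline covariate of the same measure. The protocol gives a prognostic reason for stratifying by sex only, and sex is the factor it keeps. A full covariate list is also often settled in the analysis plan.

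Most of this stands, and it is why the point is minor. The size depends wholly on centres differing after baseline adjustment. Losses of several points of power need f of 10 to 20%, which the protocol gives no reason to expect. Two parts do not carry. The section does name its terms and includes one stratification factor while leaving out the other, so it is not silent on the matter. Nor is a small f evidence for omission: local staff deliver the diet and exercise advice, scanners are local, and some recruitment routes are specific to Toronto, so f need not be zero.

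**Conclusion.** The mismatch is real and minor. If centres do not differ after baseline adjustment, omitting centre has no effect. If they account for 2 to 5% of the residual variance, about 0.3 to 0.9 points of power are forgone by formula at 260, or 0.5 to 1.4 at 194, whichever way the SD of 276 is read. At 260 with the SD including centre variance, the interval is 0.7 to 1.7 mm³ wider on each side than it need be (64.2 − 63.5 and 64.2 − 62.5). The error is in the conservative direction, with no bias and no excess of false positives. These figures rest on the assumed f, on the protocol's correlation of 0.6 and 30% dropout, and on dropout unrelated to centre or treatment. The lower end of the range is the more plausible.

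**What to change.** In section 12B) XVI, list treatment, sex and centre as main effects with baseline as a covariate, and define centre as a three-level fixed effect. If the analysis plan already includes centre, bring this section into line with it.

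The cost is two degrees of freedom out of about 182 completers (about 136 if 194 are randomised). If centres do not differ at all, the loss is a few tenths of a point of power at most: in the 10,000-run simulation, 90.3 to 90.2% at 260 and 78.0 to 77.7% at 194. The sample size does not change. Fixing the term before results are seen also removes any discretion over whether to adjust for centre afterwards.

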Blinding or masking the participants or the dietitians in this study is not possible due to the very different nature and physical form of the foods. The statistician will be blinded to the nature of the treatment when analyzing the data (i.e. will not know what treatment assignment 1 and 2 refer to). Physicians will not be informed of patient randomization when requested to make clinical decisions. Technicians who measure study outcomes will be blinded to the treatments, as will those who will be scoring the MRI images at the central location. It will be stressed to the participants that both dietary treatments have been considered to confer benefits. In this way the expectation of benefit from either treatment will be balanced (equipoise) (Please also see section 12B) I.).

12B) V. What are the planned inclusion/exclusion criteria?

Inclusion criteria: (Please also see 12 B) I for basic inclusion criteria) Eligible participants will be men and postmenopausal women with a $BMI \leq 40 \text{ kg/m}^2$ and who have measurable arterial thickening ($>1.2\text{mm}$) at screening (please see details of risks, Sections 12A) and 12B) I). They should also have at least 1 of the following characteristics:

- Type 2 diabetes;
- Non-diabetic subjects post MI or post percutaneous coronary intervention (angioplasty) on statin therapy;
- Hypercholesterolemic and treated with statins or have been prescribed statins but are not taking it because of either statin intolerance or have refused statin treatment.
- Raised blood pressure ($>140/90$ untreated)

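### The stated primary ANCOVA omits baseline statin use, a plausible predictor; the estimate stays valid and adjustment would bring a small, assumption-dependent gain in precision

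*Protocol*

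**What the plan says.** Protocol 12B V requires at least one of several characteristics besides arterial thickening. One is type 2 diabetes. Another is "Non-diabetic subjects post MI or post percutaneous coronary intervention (angioplasty) on statin therapy". A third is hypercholesterolemia in people who are "treated with statins or have been prescribed statins but are not taking it because of either statin intolerance or have refused statin treatment". Untreated raised blood pressure is the fourth. The trial population therefore mixes statin users with non-users, and people with and without diabetes.

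Under 12B III, participants are "randomized after stratification by centre and sex". Under 12B XVI, the primary analysis is an ANCOVA "with the 3 year value as the outcome, treatment and sex as main effects and baseline as a covariate". Neither place mentions statin use or diabetes. The exploratory analyses in 12B XVIII are by sex, site or LDL target.

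In 12B XI, the effect size rests on a cited study of increased statin dosage, with 60 mm³ less plaque volume for a 0.31 mmol/L fall in LDL-C over 6 months. Section 12B VII adds that benefits in earlier diet and statin imaging trials grew with time. Section 12B VIII lists initiation of statin therapy as a secondary outcome.

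**The concern.** The protocol's own argument is that lowering LDL-C, with a statin as the worked example, moves carotid plaque volume. On that argument, a participant's statin status at entry may say something about the year-3 value that the baseline scan does not. The scan reflects past exposure, and the sample size section assumes a baseline-to-end correlation of only 0.6, so 64% of the outcome variance (1 − 0.36) remains after baseline adjustment.

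If statin use explains part of that remainder, leaving it out has two consequences. The residual variance is larger than it need be, and a chance difference in statin use between the randomised groups passes into the diet and exercise estimates. Because 12B XVI lists the model terms, this is a stated choice of model and not only a detail left for later.

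**Working it through.** **Inputs from 12B XI and XII.** Target difference 106.5 mm³; SD 276 mm³; α = 0.05 (taken as two-sided); power 0.80; r = 0.6; dropout 30%; 194 randomised as planned, 260 as the current total.

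**Inputs assumed, because the protocol gives none.** Proportion q on statins at entry: 30 to 70%. Difference δ between users and non-users in the year-3 value, given baseline: 50 to 150 mm³. On the protocol's conversion this equals 50 × 0.31/60 = 0.26 to 150 × 0.31/60 = 0.78 mmol/L of LDL-C.

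**1. The plan's own figures.**
- Two-sample t-test: n = 2 × [276 × (1.960 + 0.842)/106.5]² = 105.4 per group (stated: 105).
- ANCOVA: 105.4 × (1 − 0.6²) = 67.5 per group (stated: 67).
- Total: 2 × 68/0.70 = 194.3 (stated: 194).

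These reproduce. A group here is one side of a factorial margin. The 81 per arm printed beside 194 does not fit and is not used.

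**2. Variance that statin use could explain.** Residual SD after baseline = 276 × √(1 − 0.36) = 220.8 mm³. The further share explained by a binary covariate is R² = q(1 − q)δ²/220.8².

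| δ (mm³) | q = 0.3 or 0.7 | q = 0.5 |
|---|---|---|
| 50 | 0.011 | 0.013 |
| 100 | 0.043 | 0.051 |
| 150 | 0.097 | 0.115 |

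**3. Power.** Power = Φ(106.5/[220.8 × √(1 − R²) × √(2/n)] − 1.96).

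| Completers per margin | Unadjusted | R² = 0.011 | R² = 0.115 |
|---|---|---|---|
| 67 | 79.7% | 80% | 84% |
| 91 (260 × 0.70/2) | 90.2% | 90.5% | 93% |

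**4. Chance imbalance.** The 95% limit for the difference in statin use between two groups of m is 1.96 × √(2q(1 − q)/m).
- 97 versus 97 (194 randomised): 13 to 14 percentage points. Multiplied by δ, the unadjusted estimate shifts by 6 to 21 mm³, or 6 to 20% of 106.5.
- 130 versus 130 (260 randomised): 11 to 12 points, a shift of 6 to 18 mm³, or 5 to 17%.

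Relative to the standard error this limit is 1.96 × √R², whatever the group size: 1.96 × √0.011 = 0.2 to 1.96 × √0.115 = 0.7 standard errors. It is the extreme of a random fluctuation, and the ordinary confidence interval already allows for it.

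**The case against.** The strongest reply is that nothing is wrong. Under randomisation, an ANCOVA on treatment, sex and the baseline outcome is unbiased and keeps its type I error, and further covariates are a matter of preference that a statistical analysis plan may settle. The first part stands in full. The second stands only in part, because 12B XVI writes out the terms, and a later plan that added covariates would depart from that sentence.

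Three stronger readings are tempting, and the document supports none of them.

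- A reader might infer that statin use is an established, major predictor of the 3-year course. The cited 60 mm³ followed an increase in dose over 6 months. It does not compare stable users with non-users at entry. Recruitment under 12B XII also asks that no lipid-treatment change be anticipated for the next 6 months. Users may be the higher-risk participants, so even the sign of the difference is open.
- A reader might infer the same for diabetes or a previous infarction. The protocol gives no evidence that either affects the course of wall volume.
- A reader might fault the randomisation for not stratifying on statin use. Stratifying by centre and sex is a legitimate choice, and 12B XII reports that the recruitment target has been reached and exceeded, so the model is where anything can still be done.

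Further points stand. The assumed 150 mm³ exceeds the trial's whole target effect. The planning SD draws on a statin study and a diabetes cohort, so some of this variation is probably already inside the 80% power; omission forgoes a gain and does not push power below plan. The range for q follows 12B V, whereas 12B I describes people who need no drug treatment; those sections must be reconciled, and fewer statin users than assumed would shrink the gain. Finally, a baseline covariate does nothing about statins started during follow-up.

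**Conclusion.** The point holds as a minor improvement in efficiency. The present primary analysis is valid; the omission costs some avoidable residual variance and leaves the estimate open to a chance imbalance that could have been adjusted for.

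Under the assumed ranges, the gain is about 0.5 to 4 power points at the planned size. At the current total of 260, where power is already about 90%, it is about 0.3 to 3 points. If statin use adds little beyond baseline wall volume, the gain is close to nil. Support for the statin covariate is indirect: the protocol's effect-size argument, and its statement that imaging benefits grew over time. For diabetes the document gives no support, so that covariate is optional.

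**What to change.** In 12B XVI, before unblinding, add baseline statin use (yes/no) as a prespecified covariate in the primary ANCOVA and, optionally, type 2 diabetes (yes/no). Put the same terms in the multiple-imputation model so that it matches the analysis model. Keep the present model, with treatment, sex and baseline only, as a sensitivity analysis.

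The cost is one sentence and one or two degrees of freedom. Baseline statin status has to be known for every participant anyway in order to score statin initiation, and both covariates are fixed before randomisation, so adjusting for them introduces no bias. The downside is that the gain may prove negligible.
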